Currently, no studies have evaluated an incentive-based abstinence intervention beyond one month among non-treatment seeking adolescents. The long-term goal of this line of research will address critically important clinical questions of the impact of cannabis use, and particularly the potential beneficial effect of long-term cannabis abstinence, on learning/cognition and, more importantly, real-world academic functioning in adolescents. That is, to understand whether six months of abstinence results in an improvement in cognitive performance among adolescents who use cannabis regularly. This is a highly relevant question, as the perception among adolescents and often their parents/guardians, is that cannabis use does not impact their ability to learn and perform in school. It has the potential to have profound impact on our understanding of the clinical effect of cannabis on cognition in young people as well on policy, given the rapidly shifting political landscape on cannabis use in the US that will no doubt have a strong impact on prevalence and frequency of adolescent cannabis use, regardless of age restrictions on purchase.

This study is a critically important first-of-its-kind investigation of the potential research utility of using contingency management to examine long-term changes in cannabis use with six months of abstinence. These pilot data will inform a later trial which will focus on testing the longitudinal relationships between adolescent cognition and cannabis use, questions of high and growing public health significance given adolescents' increased access to cannabis with legalization.

II. SPECIFIC AIMS

This pilot study will:

Phase 0

Aim 1: Evaluate the acceptability and feasibility of a contingency management intervention for six months of biochemically verified cannabis abstinence in adolescents who use cannabis at least once per week and who are not seeking treatment.

Aim 2: Compare the initial efficacy of two different, non-randomized, contingency management intervention payment schedules (high vs low) to determine which produces more consistent rates of long-term abstinence.

Phase 1

Aim 1: Collect preliminary data on whether six months of cannabis abstinence is associated with improvement in cognitive functioning among frequent adolescent cannabis users

III. SUBJECT SELECTION

Inclusion Criteria:

1. Male and female adolescents who are between the ages of 13 and 20 (inclusive);

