- **Adolescents Recruited and Enrolled from the Community: Waived Parental Consent for Telephone Screening.** Potential participants will be recruited via online advertisements, community flyers (see recruitment materials), and databases of participants from other lab protocols who have given explicit consent to be re-contacted for new studies. Among participants who are determined eligible through the telephone screening, under the age of 18, and interested in participating in the study, parent/legal guardian contact information will be collected to obtain informed consent for the active study phase. No active study procedures will be conducted with potential participants prior to obtaining written parent/guardian informed consent and adolescent assent for those under the age of 18 or written consent for those 18 years of age or older.

A waiver of written consent for telephone screening only is requested and is justified given the following:

- **The proposed research involves no more than minimal risk to participants.** During telephone screening, we will provide details about the study and ask potential participants if they have any questions or concerns about the study protocol. We will also ask participants basic demographic information as well as brief questions related to frequency and recency of cannabis use to determine eligibility. These questions are indistinguishable from questions asked during standard school substance use assessments. This telephone screener is anticipated to take no more than 10 minutes and participants are free to refuse to answer any questions. They will be told that all information will be kept strictly confidential and answers to telephone screening questions will be stored separately from any identifying information. If participants are interested in the study and are eligible, we will collect parent/guardian contact information so that we can obtain written parental consent for study enrollment. No study procedures will occur before written parental consent is obtained (parental consent if under the age of 18). We will also obtain written adolescent assent (if under the age of 18) or consent (if 18 years of age or older) at the baseline visit, prior to the initiation of any study procedures, during which time we will review the study in detail.

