of 18 until the parental consent form is obtained. Within the consent form is a description of collection of saliva samples for genetic analysis; parents can decline consent for DNA without penalty on participation for the rest of the project. During the initial study visit, informed assent will be obtained from the student by a trained member of the study staff prior to administering any study procedures. As in the parental consent form, students will indicate on the assent form whether they permit collection and analysis of genetic samples. All participants will be given the opportunity to ask questions to a doctoral-level member of the study staff during the assent process. Contact information of key MGH study staff will be provided and participants (and parents/guardians) will be informed that the co-investigators are available to answer any questions or concerns they may have about the study. All participants will be provided with a copy of their signed parental consent and student assent forms.

Students who are interested in participating and are over 18 years old will be contacted by a member of study staff, who will coordinate the initial study visit. At the time of such visit, informed consent will be obtained by a trained member of the study staff prior to administering any study procedures. Within the consent form is a description of collection of saliva samples for genetic analysis; participants can decline consent for DNA without penalty on participation for the rest of the project. All participants will be given the opportunity to ask questions to a doctoral-level member of study staff during the consent process. Contact information of key study staff will be provided and participants will be informed that the co-investigators are available to answer any questions or concerns they may have about the study. All eligible participants will be provided with a copy of their signed consent form.

Upon study enrollment to Phase 0, all participants will be assigned to either a high (\$1,235) or low (\$910) contingency management payment schedule in order to collect data that informs us on the level of payment most likely to make long-term abstinence feasible and reliably attainable (about 80% abstinence).

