- **Adolescents Recruited and Enrolled from the Community: Waived Parental Consent for Telephone Screening:** In response to community advertisements, potential participants will call the laboratory to inquire about details of the study and complete a brief telephone questionnaire that will include general demographic items as well as basic questions related to health behavior such as frequency and recency of cannabis and alcohol use. Eligible and interested participants under the age of 18 will be asked for parent/guardian contact information to coordinate obtaining written parental informed consent. Eligible and interested participants age 18 and older will schedule their baseline study visit with MGH staff and informed consent will be obtained directly from these participants at their baseline visit. A screening log that includes a non-identifying subject ID, the date of screening, eligibility status, and enrollment decision/status will be kept for all individuals screened.

Active Study Phase (The Epiphany School and Millis, Medford, Walpole, Westford, and Cambridge Public Schools; Community)

The active study procedures for both Phase 0 and Phase 1 will be identical with the exception of added cognitive assessments and parent/guardian questionnaires for Phase 1 of the study. Phase 1 will not begin until the completion of Phase 0. Interested participants under the age of 18 who provide informed assent and have a parent/guardian who provides informed consent, and participants over the age of 18 who provide informed consent, will be enrolled in the active phase of the study. All participants will complete identical study procedures.

Upon study enrollment participants will be placed into either the high or low payment schedule. All participants will complete 26 study visits, which will be spaced across approximately six months, or 24 weeks (see Study Schema and Time and Events table), and will be conducted confidentially at the participant's school or in the laboratory at MGH. In rare circumstances (eg. shortage of available rooms on school campus), we may request that study visits be conducted in a private space in the near-by public library. Parents of students under the age of 18 who are recruited from one of the participating schools will be notified ahead of time for any visits not conducted on school grounds.

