- 4) Genetic data are encoded using coded identifiers. These codes, rather than personal identifiers, are used in any analytic datasets. The code key linking coded identifiers to personal identifiers are kept in an access-restricted, password protected electronic file and are not shared with the genetics laboratories.
- 5) Consent forms are stored in locked cabinets apart from demographic and diagnostic data.
- 6) Samples and genetic data stored in the laboratory will be identified only by the code numbers and laboratory personnel will not have access to personal identifiers.
- 7) The most serious risk would be identification of individuals in the publicly shared database. To prevent this, computerized data files provided to other investigators will not include any of the HIPPA-defined personal identifiers. Published material will not identify subjects.

VI. BIOSTATISTICAL ANALYSES

This is a first-of-its kind study using a 6-month contingency management paradigm for cannabis abstinence. As such, pilot testing needs to occur to evaluate feasibility of this paradigm before a larger trial can be proposed. Phase 0 will examine the initial acceptability and feasibility of a contingency management protocol for long-term abstinence, and collect preliminary data on the efficacy of two competing payment schedules. We will calculate continuous abstinence rates at six months. If continuous abstinence rates at six months are low (e.g. below 80 percent) and therefore a larger six-month trial is not likely feasible, we will then examine continuous abstinence rates at each prior month of the study. This will help us determine the longest trial feasible in this population. Phase 1 will collect pilot data on change in cognition with six months of abstinence, using the payment schedule informed by Phase 0. These data will be used to estimate effect sizes and inform a subsequent power analysis for a fully-powered, randomized trial to be proposed at the completion of this pilot study.

VII. RISKS AND DISCOMFORTS

There are a few potential risks to individuals participating in the study.

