The table below details the maximum potential earnings; however, the total amount earned will depend on the number of sessions attended, and also for evidenced cannabis abstinence.

Phase 0 Schedule of Compensation

Month	Visit Number	Schedule	
		Low	High
1	0	Screening	\$0
	1	Week 0 (V1)	\$10 (attendance)
	2	Week 0 (V2)	\$12
	3	Week 1 (V3)	\$14
	4	Week 2	\$16
	5	Week 3	\$18
2	6	Week 4	\$20
	7	Week 5	\$22
	8	Week 6	\$24
	9	Week 7	\$26
3	10	Week 8	\$28
	11	Week 9	\$30
	12	Week 10	\$32
	13	Week 11	\$34
4	14	Week 12	\$36
	15	Week 13	\$38
	16	Week 14	\$40
	17	Week 15	\$42
5	18	Week 16	\$44
	19	Week 17	\$46
	20	Week 18	\$48
	21	Week 19	\$50
6	22	Week 20	\$52
	23	Week 21	\$54
	24	Week 22	\$56
	25	Week 23	\$58
	26	Week 24	\$60
	Totals		\$910
		\$1235	

Participants may also receive reimbursement for transportation to our center in Boston. They may receive \$2.00 per ride on the bus or \$2.90 per ride on the subway. Payment will be provided on the CT Payer reloadable card on the day of the study visit. If a parent accompanies their child to the study visit, they may be

reimbursed for transportation at the same rate. Parking vouchers are also available for participants or their parents who drive to our center and park in an MGH parking garage.

The payment schedule for Phase 1 will be informed by data collected during the Phase 0 pilot period. This protocol will be amended upon completion of Phase 0 to designate the payment schedule to be employed.

XI. REFERENCES

1. Johnston, L.D., et al., Monitoring the Future national survey results on drug use: 1975-2017: Overview, key findings on adolescent drug use. Ann Arbor: Institute for Social Research, The University of Michigan., 2017.
2. Johnston, L. D., Miech, R. A., O'Malley, P. M., Bachman, J. G., Schulenberg, J. E., & Patrick, M. E. (2018). Monitoring the Future national survey results on drug use: 1975-2017: Overview, key findings on adolescent drug use. Ann Arbor: Institute for Social Research, The University of Michigan.
3. Cohen, P. J. (2010). Medical marijuana 2010: It's time to fix the regulatory vacuum. *The Journal of Law, Medicine & Ethics*, 38, 654-666.
4. Burgdorf, J. R., Kilmer, B., & Pacula, R. L. (2011). Heterogeneity in the composition of marijuana seized in California. *Drug and Alcohol Dependence*, 117, 59-61.

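### Aim 2 compares two payment schedules without randomization, a stated assignment rule or a baseline table, so who is placed on each could tilt the Phase 1 choice.

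*Combined protocol and SAP*

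**What the plan says.** Section II, Phase 0 Aim 2, is to "Compare the initial efficacy of two different, non-randomized, contingency management intervention payment schedules (high vs low) to determine which produces" the more consistent long-term abstinence. The design is thus openly non-randomized.

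Placement is mentioned in three places. Section IV has the same sentence for school recruits and for community recruits: "Upon study enrollment to Phase 0, all participants will be assigned to either a high" ($1,235) or low ($910) schedule, so as to learn "the level of payment most likely to make long-term abstinence feasible and reliably attainable (about 80% abstinence"). Section V, Active Study Phase, says: "Upon study enrollment participants will be placed into either the high or low payment schedule". None of them gives a rule, a ratio, the person who assigns, or whether that person knows the participant's level of use.

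Section VI plans continuous abstinence rates at six months, and at earlier months if the six-month rate is low (for example, below 80 percent). It gives no method for comparing the schedules, no adjustment, and no table of baseline characteristics by schedule.

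The result is used. Section VI has Phase 1 "using the payment schedule informed by Phase 0". Section X says "The payment schedule for Phase 1 will be informed by data collected during the Phase 0 pilot period" and "This protocol will be amended upon completion of Phase 0 to designate the payment schedule to be employed".

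**The concern.** Calling the assignment non-randomized says what will not be done; it does not say what will be done. Alternation, calendar blocks and staff discretion all fit the description and carry very different risks of selection.

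The groups could differ in several ways:

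- **Use frequency.** Section III sets a minimum of once a week and no maximum. Screening records frequency and recency of use before enrolment, so staff can know a person's use level when placing them.
- **Recruitment source.** Participants come from schools, community advertising, and "databases of participants from other lab protocols who have given explicit consent to be re-contacted for new studies".
- **Previous practice at abstaining.** The DNA collection text in Section V shows that people who completed the one-month abstinence study may enrol.
- **Calendar time**, if one schedule is filled before the other.

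A systematic difference on any of these could shift the High–Low comparison and each schedule's own rate against the 80% mark, in either direction. The baseline data that would help reveal it are collected (90-day timeline follow-back and CUDIT-R at Visit 1), but no tabulation by schedule is planned.

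**Working it through.** The plan gives no power, effect size or expected abstinence rate for Phase 0, so there is no stated figure on this point to reproduce. The payment totals do reproduce: 26 visits starting at $10 and rising by $2 sum to $910, and rising by $3 to $1,235. The difference is $325 per participant.

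The rest is an illustration of size. **From the documents:** 10 participants in Phase 0, two schedules, a mark of about 80%. **Assumed:** 5 per schedule; 5 lighter and 5 heavier users; no payment effect; lighter/heavier abstinence of 70/50, 80/40 or 90/30 percent.

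**Step 1: what an unequal mix does.** Suppose 4 of the 5 lighter users are on High. With p_L and p_H for lighter and heavier users, expected abstinence is (4p_L + p_H)/5 on High and (p_L + 4p_H)/5 on Low. At 70/50 that is (2.8 + 0.5)/5 = 66% and (0.7 + 2.0)/5 = 54%. The number of abstainers on each schedule is a sum of two binomials, computed exactly.

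| Lighter/heavier | Expected High / Low | High leads | Low leads | At least 4 of 5: High / Low |
|---|---|---|---|---|
| 70/50 | 66% / 54% | 53% | 23% | 45% / 24% |
| 80/40 | 72% / 48% | 70% | 11% | 57% / 15% |
| 90/30 | 78% / 42% | 86% | 3% | 74% / 8% |

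The last column reads the 80% mark as at least 4 of 5. The gap is 12 to 36 points with no payment effect. These figures are conditional on the 4:1 mix. Randomization does not change them; it changes how often such a mix arises.

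**Step 2: how often the mix arises.** Let w be a lighter user's odds of being on High relative to a heavier user's. The chance of k lighter users on High is proportional to C(5,k) · C(5,5−k) · w^k. The chance that k is 4 or 5 is:

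- w = 1 (random): (25 + 1)/252 = 10%
- w = 2: (400 + 32)/1683 = 26%
- w = 3: (2025 + 243)/5944 = 38%

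**Step 3: the like-for-like comparison.** Averaging over all mixes, for abstinence from 70/50 to 90/30:

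| Assignment | Expected High–Low gap | High leads | Low leads |
|---|---|---|---|
| Random (w = 1) | 0 points | 37–38% | 37–38% |
| w = 2 | 3.8 to 11.4 points | 42–52% | 33–25% |
| w = 3 | 6.0 to 17.9 points | 45–61% | 30–19% |

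This table, not Step 1, shows the effect of the assignment process. The odds ratios are assumptions; a tilt toward Low would mirror them.

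**Step 4: what randomization cannot do.** In random lists, a 4:1 or worse mix in either direction arises with probability (1 + 25 + 25 + 1)/252 = 52/252 = 21%. With a true 80% versus 60% and 5 per schedule, the better schedule leads in 64% of randomized trials, the worse in 14%, and they tie in 22%.

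**The case against.** The strongest reply is that this is a 10-person pilot that says what it is. Aim 2 speaks of initial efficacy, Section VI of preliminary data, no between-schedule test is planned, and the Phase 1 schedule must be named by amendment. A randomized, fully powered trial is to follow. Nothing in the documents links schedule to use level, recruitment source or date, and every input to the illustration is assumed.

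The arithmetic also supports part of this reply. With 5 per schedule one participant is 20 points, so every averaged gap in Step 3 is smaller than one person. With no payment effect, one schedule still leads by chance in about 75% of randomized trials, against 75% to 77% at w = 2 and 75% to 79% at w = 3. Randomization removes the direction of the tilt but barely reduces how often Phase 0 points to a difference that is not there.

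Much of that stands. Imprecision is the main limit, non-random assignment can be acceptable in a pilot this small, and no imbalance is shown. It does not answer the omission. Small numbers explain why the comparison is imprecise; they do not justify adding an avoidable and undocumented source of systematic error to data that will inform a choice. It is also fair to say that randomizing helps only if some Phase 0 participants are still unassigned, which the documents do not settle.

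**Conclusion.** The concern holds. Aim 2 sets out to determine the better schedule from groups formed by an unstated, non-random process, with no planned look at whether they were alike, and the result informs Phase 1. The omission is certain from the text; a tilt is a possibility, not a prediction.

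Under the assumptions above, placement that doubles or triples a lighter user's odds of one schedule produces an expected gap of about 4 to 18 points with no payment effect. The consequence is bounded: no decision rule is stated, at most $325 per participant separates the schedules, Phase 1 plans 20 participants, and an amendment is needed before it proceeds with a named schedule. The change should be made because it is cheap, not because the harm is large.

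**What to change.** 1. **Assignment (Sections IV and V, wherever placement is described).** State: *Phase 0 participants not yet assigned will be randomized 1:1 from a concealed list, with block size not disclosed to enrolling staff. Each allocation is opened at Visit 1 after consent, re-confirmation of eligibility and the baseline interview and questionnaires, and before the behavioral contract.* This is workable because both schedules pay $10 at Visit 1 and first differ at Visit 2 ($12 versus $13).
2. **Participants already assigned.** Document the rule that was used and report them separately from those randomized. If all 10 are already assigned, only this documentation, the table and the wording change apply.
3. **Section VI.** Add: *Baseline 90-day cannabis use, CUDIT-R, prior completion of the one-month study, recruitment source and enrolment date will be tabulated by schedule; abstinence by schedule will be reported descriptively.*
4. **Aim 2.** Say describe instead of determine, and randomized instead of non-randomized (or describe the mixed assignment if some were already placed).

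The cost is one list, a short amendment and one table, with no added visits or participants; the timeline follow-back and CUDIT-R are already collected at baseline. Item 1 assumes that some participants remain unassigned. Section X treats completion of Phase 0 as still to come, but enrolment status is not given. Consent and assent materials would have to cover both payment amounts before allocation is known, since Section X relies on parents knowing what can be earned; whether they already do cannot be seen here. Chance imbalance will remain with 10 people, which is why items 3 and 4 are needed even with randomization.

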Scheduled Visits (Approximately 10 to 120 minutes per visit). The first week of the study will consist of three visits: an initial baseline visit (during which eligibility will be re-confirmed), a mid-week visit (Visit 2), and a visit occurring approximately 1 week following baseline (Visit 3). Participants will then complete visits occurring at Week 2 (Visit 4) and every week thereafter, totaling 26 scheduled visits. The main objective of Phase 0 will be to assess the acceptability and feasibility of a contingency management protocol for long-term abstinence and to pilot two competing payment schedules. Visits will therefore be brief and impose minimal burden on participants. All scheduled visits during this phase will only consist of self-report questionnaires, semi-structured assessments of mood and substance use, and urine drug tests to verify abstinence. During Phase 1 of the study, cognitive testing will take place at scheduled visits occurring at baseline (Visit 1), Week 4 (Visit 6), Week 8 (Visit 10), Week 12 (Visit 14), Week 16 (Visit 18), Week 20 (Visit 22), and Week 24 (Visit 26). In addition, parents/guardians will be asked to answer brief questionnaires about their child's behavior and mood during Phase 1 at scheduled visits occurring at baseline (Visit 1), Week 4 (Visit 6), Week 12 (Visit 14), and Week 24 (Visit 26).

At the baseline visit (Visit 1), all participants will be using cannabis as usual. At the end of baseline, all participants (N=20) will be asked to abstain from cannabis use for six months and will complete a behavioral contract²⁶ that lists behaviors to be monitored, schedule of monitoring, and contingencies to be imposed (see section X for more details on payment contingencies). All compensation for attendance will be distributed at the end of each study visit, and will be distributed between study visits for abstinence.

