Cannabis abstinence will be indexed by self-reported non-use and, given cannabis' long half-life, by progressively decreasing quantitative levels of 11-nor-delta-9-THC-9-carboxylic acid (THCCOOH), the primary cannabis metabolite, in urine. Residual cannabinoid excretion will be differentiated from new cannabis exposure using a statistical model developed by Schwikle and colleagues.²⁷ This model was empirically derived from urine CN-THCCOOH concentration ratios of consecutively collected specimen pairs (current specimen/prior specimen). This model takes into account the time between collection of specimens, which enhances the accuracy of prediction of new cannabis use.²⁸⁻³⁰ This formula yields an expected CN-THCCOOH ratio associated with specimen pairs during abstinence, and observed ratios that exceed this expected value are interpreted as new cannabis use.

All study procedures will take place at the participant's school or in the laboratory at MGH, with the exception of laboratory processing of cannabis metabolites, which will be conducted at Dominion Diagnostics.

Assessment Techniques

See Time and Events Table for a detailed schedule of assessments administered by visit and by study phase.

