In Phase 1 of the study, we will explore whether six months of cannabis abstinence may be associated with changes in neurocognitive functioning such as verbal learning/memory, attention, working memory, and complex decision-making. Studies show differences in these domains between cannabis users and non-users.³¹⁻³² Additionally, the neurobiological substrates typically implicated in performance on these tasks (e.g., prefrontal cortex, fronto-subcortical circuitry) undergo the most protracted development during adolescence and may therefore be most susceptible to insults from exogenous cannabinoids. We are proposing to do much of the cognitive testing with the Cambridge Neuropsychological Test Automated Battery (CANTAB). We specifically selected the CANTAB, which is a “state-of-the-art” cognitive battery, based on several criteria to address practical and methodological concerns that may arise from a longitudinal, non-laboratory study. First, the CANTAB has been validated in many populations (including substance using adolescents³³) and normative data are available. The CANTAB is also administered on a small computerized touch screen tablet, which allows for easy portability, efficient testing of many people (essential for study feasibility), and standardized administration. Third, tests have been adapted from animal model paradigms to increase translatability of findings and tests can be analyzed based on their cognitive components to more readily define impaired and spared cognitive capacities. Next, neuroimaging studies are available that show reliance on neural circuitry implicated in cognitive functioning and addiction. Finally, the CANTAB has been validated longitudinally and offers the unique advantage of parallel forms for retest. The cognitive battery will be administered at the baseline visit (Visit 1), Week 4 (Visit 6), Week 8 (Visit 10), Week 12 (Visit 14), Week 16 (Visit 18), Week 20 (Visit 22), and Week 24 (Visit 26).

Drug Testing: Participants will provide a urine sample at all study visits to qualitatively screen for cannabis use as well as other substances of abuse and to quantitatively screen for amount of THC metabolites in urine.

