Phase 0: Participants will be reimbursed using one of two different payment schedules, both escalating based on continuous cannabis abstinence (indexed by self-reported non-use and progressively decreasing quantitative levels of urine THCCOOH). Compensation for attendance to the baseline visit (Visit 1) will be distributed at the end of the study visit, and all compensation for abstinence will be distributed between study visits upon receipt of laboratory results from Dominion Diagnostics. Participants are reset to the starting level if abstinence is not demonstrated within the first week of study participation. If a participant fails to demonstrate abstinence at any point between Week 1 (Visit 3) through the last visit, they will be discontinued from the study based on non-compliance with study protocol.

The schedule of reimbursement for session attendance and abstinence (see payment schedule below) was informed by the payment schedule utilized by our current one-month abstinence protocol (Protocol #: 2015P000076). In our one-month abstinence protocol, the schedule of reimbursement is what has been found effective in similar populations.³⁴⁻³⁸ All participants will be paid 10 dollars for attending the Baseline visit (Visit 1). After the initial baseline visit, the "Low" payment group will receive payments escalating 2 dollars for each subsequent visit with verified abstinence (e.g., \$12, \$14, \$16). The "High" payment group will receive

escalating payments of 3 dollars for continuous abstinence following the baseline payment (e.g., \$13, \$16, \$19). The schedules of reimbursement for session attendance and abstinence for the current six-month study - \$910 or \$1,235 – are *more* conservative than the amount of reimbursement estimated should payment from our one-month abstinence protocol be extended to six months. That is, the current protocol proposes to compensate more than \$4,300-4,600 less than that estimated should the compensation schedule from Protocol #2015P000076 be extended to six months.

The total amount of reimbursement is thought to be appropriate in this population for the following reasons: 1) parents/guardians will be aware of the amount of money that participants can potentially earn by participating in the study; 2) all participants will be incentivized to abstain from a health-compromising behavior, that is continued use of cannabis; 3) CT Payer greatly minimizes risk of funds being used for illegal purchases.

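### Does leaving the urine-ratio cut-off and its error rate unstated make the continuous-abstinence rate unreliable?

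*Combined protocol and SAP*

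**What the plan says.** Section V (Scheduled Visits) indexes abstinence by self-reported non-use together with falling urine THCCOOH. To separate residual excretion from new use it adopts a cited model (reference 27) built on the ratio of the current specimen to the prior one, allowing for the time between them. The decision rule is that "observed ratios that exceed this expected value are interpreted as new cannabis use". Under Drug Testing, a urine sample is taken at every visit "to qualitatively screen for cannabis use as well as other substances of abuse and to quantitatively screen for amount of THC metabolites in urine".

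Section X (Phase 0) repeats the index for payment: abstinence is "indexed by self-reported non-use and progressively decreasing quantitative levels of urine THCCOOH". It sets two consequences. Early on, "Participants are reset to the starting level if abstinence is not demonstrated within the first week of study participation". The later consequence is for anyone who "fails to demonstrate abstinence at any point between Week 1 (Visit 3) through the last visit, they will be discontinued from the study". Section V says that "The first week of the study will consist of three visits", the third being Visit 3, so the two consequences overlap at that visit.

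Section VI calculates continuous abstinence at six months. Its benchmark is worded as an example: "If continuous abstinence rates at six months are low (e.g. below 80 percent"). In that case, "we will then examine continuous abstinence rates at each prior month of the study", to find the longest feasible trial. Phase 0 aims for 10 participants (Section IV).

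**The concern.** Three details are missing. First, *expected* could mean the middle of the ratio distribution during abstinence or an upper limit of it, and the false-flag rates of these two differ enormously. Second, no false-positive or false-negative rate is given. Third, a ratio cannot be formed, and a level cannot keep falling, once a specimen is below quantification; with at-least-weekly users tested for about 24 weeks, such specimens are foreseeable. It is also not stated how the qualitative cannabis screen relates to the ratio.

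These gaps would matter because a single failure is final. A small per-test error compounds over the visits, so it lowers the six-month rate more than the earlier monthly rates. A fully abstinent group could then appear to fall below 80%, and the monthly fallback could suggest that abstinence fades with time. The title of the model's source refers to chronic, daily users, which adds doubt about whether its error rates apply to this trial.

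**Working it through.** **Number of tests.** Three first-week visits plus Weeks 2 to 24 (23 visits) give 26, as Section V states. The payment totals agree: the sum of 10 + 2k for k = 0 to 25 is 910, and the sum of 10 + 3k is 1,235, matching the Section X table. Visits 3 to 26 are 24 tests on which failure is final, or 23 if a Visit 3 failure only resets payment.

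**Accumulation.** Let f be the per-test false-flag rate in a true abstainer. The documents do not give f; every value below is an assumption. With independent tests, the share of true abstainers passing k tests is (1 − f)^k.

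| f | k = 24 | k = 8 |
|---|---|---|
| 0.1% | 97.6% | 99.2% |
| 0.5% | 88.7% | 96.1% |
| 1% | 78.6% | 92.3% |
| 2% | 61.6% | 85.1% |
| 5% | 29.2% | 66.3% |

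The column k = 8 illustrates what happens if undetectable specimens count as abstinent and only 8 tests can still produce a flag. With k = 23 and f = 1% the share is 79.4%.

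**Break-even with 80%.** f = 1 − 0.8^(1/k), which is 0.93% for k = 24 and 2.75% for k = 8.

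**Dependence.** Adjacent ratios share a specimen. Simulating this gives 78.4% instead of 78.6% at f = 1%. A within-person correlation of 0.5 gives about 88%. Independence is therefore either close to right or pessimistic here.

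**Monthly pattern.** By the Section X table, the tests completed from Visit 3 to the end of months 1 to 6 number 3, 7, 11, 15, 19 and 24. At f = 1% the passing share falls from 97% at month 1 to 79% at month 6. At f = 0.21% it runs 99, 99, 98, 97, 96 and 95%.

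**The central-value reading.** If the cut-off were a median, f would be 50%, and 0.5^3 = 12.5% of true abstainers would survive the first month. A rule that discontinues people on this test could not be run that way, so an upper limit is the natural reading.

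**Net direction.** If 80% truly abstain and a share m of lapsers pass every test, the observed rate is 0.8(1 − f)^24 + 0.2m. At f = 0.21%, (1 − f)^24 = 0.95, so the rate is 76% with m = 0 and returns to 80% with m = 0.20. Neither f nor m is known.

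**Against sampling error.** The exact 95% interval for 8 of 10 is 44% to 97%. The chance of seeing at least 8 of 10 is 68% at a rate of 80% and 56% at 76%.

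**The case for a change.** The strongest case for a change is that two analysts could obtain different rates from the same specimens. The source may define limits, but the protocol does not say which one it applies. If all 10 participants were abstinent, the chance of observing at least 8 of 10 would be 63% at f = 1% and 19% at f = 2%. Each misclassified person moves the rate by 10 points. Phase 0 also informs the Phase 1 payment schedule, and a limit chosen late could be steered by the results.

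Part of this stands: the limit and the treatment of undetectable specimens are not written down. The rest is weaker.

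- Adopting a cited model by reference is ordinary in a pilot protocol, and nothing shows that the model leaves its limit open.
- The population point rests on one title. At-least-weekly use includes daily use, and Section V also cites work (reference 28) whose title concerns adolescents treated for marijuana use disorders.
- Falling THCCOOH is followed directly by the model that puts it into operation. Nothing makes the qualitative screen a second abstinence criterion.
- Late steering is limited. Section X pays for abstinence between visits as laboratory results arrive, so the classification has to be applied as the trial runs.

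The possible remedies bring little. A 5% cumulative false-flag rate over 24 tests needs f = 1 − 0.95^(1/24) = 0.21% per test. If log ratios during abstinence were normal with an assumed SD of 0.2 to 0.6, that limit would lie exp((2.858 − 1.645) × SD) = 1.3 to 2.1 times above a 5% limit. Small lapses would then be missed in a study whose aim is biochemically verified abstinence. Nor can a separate limit for the analysis recover people already discontinued. They have no later specimens, so the rate could only be bounded, with bounds that widen by 10 points per person.

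**Conclusion.** No change to the plan follows. The text omits the type of limit, its error rate and a rule for specimens below quantification, and false flags would accumulate if they occurred. But no stated rule is shown to give a wrong result. The assumed range of 0.1% to 5% per test moves the share of true abstainers passing 24 tests from 97.6% to 29.2%, and the documents do not place f anywhere in that range. The net bias has no known sign.

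The missing details have sensible defaults: take the limit from the cited model, read it as an upper limit, and count undetectable specimens as abstinent. The last of these also reduces the number of tests that can produce a flag. With 10 participants and a benchmark given only as an example, the Phase 0 rate cannot support a fine decision at 80% under any limit. Trading sensitivity for fewer false flags is a judgement on which either side is defensible.

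The overlap at Visit 3 between payment reset and discontinuation is a wording matter for the sponsor to reconcile. Here it changes 24 tests to 23, and 78.6% to 79.4% at f = 1%.

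This conclusion assumes that the cited model supplies a usable upper limit, which the documents neither confirm nor contradict.
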